#### 5.1.4 Pre-specified supportive efficacy analysis set (PEAS)

All patients randomized and treated (at least one dose of the study treatment), and have at least one observed KCCQ-PLS assessment at both baseline and post-baseline (excluding safety follow-up), excluding those with no physical limitation at baseline (baseline KCCQ PLS = 100 or baseline PGIS as “no limitation”), will be valid for this supportive efficacy analysis set. The primary efficacy analysis will be repeated on PEAS as a supportive analysis.

### **5.1.5 Safety analysis set (SAF)**

All patients that received at least one dose of study treatment (vericiguat or placebo). Analyses will be based on actual treatment received, and patients who received both vericiguat and placebo by mistake will be assigned to the planned treatment. All safety analyses will be based on the SAF.

### **5.1.6 Per protocol set (PPS)**

All patients who meet the major inclusion and exclusion criteria at randomization that may affect efficacy, who are not taking excluded concomitant medications during the study that could have an effect on efficacy, have the KCCQ assessed at baseline and at least once during the treatment phase and who are at least 80% compliant with study medication and show no major protocol deviations. The PPS will only be used in the supportive analysis.

Major protocol deviations leading to exclusion from PPS include:

- Overall compliance with study treatment intake of <80% or >120%.
- Study medication was interrupted for more than 10 consecutive days
- No history of chronic heart failure.

A complete list of all validity findings and important protocol deviations leading to exclusion from the PPS will be specified in the Assessment Criteria Identification Requirement (ACIR).

### **5.1.7 Pharmacokinetics analysis set (PKS)**

All patients with at least one valid pharmacokinetic concentration will be included in the statistical evaluation of pharmacokinetics.

### **5.1.8 Validity Review**

A validity meeting will be held before final database closure where subject validity for the individual analysis sets will be decided. The results of the validity meeting will be documented and may comprise decisions and details relevant for statistical evaluation. Any changes to the statistical analysis prompted by the results of the validity review meeting will be documented in an amendment or in a supplement to this SAP, as applicable.

## **6. Statistical Methodology**

### **6.1 Population characteristics**

Population characteristics will be summarized overall and by treatment group. Analyses will be performed in the FAS unless otherwise noted.

#### **6.1.1 Disposition**

The number of patients enrolled, randomized, and valid for the FAS, FAS-KCCQ, FAS-6MWT, SAF, PPS and PKS will be summarized overall and by treatment groups. The number of patients discontinuing the screening phase together with the primary reason for discontinuation will be presented. The number of patients discontinuing the treatment and

follow-up phases together with the primary reason for discontinuation will be presented by treatment groups and overall in separate tables.

### **6.1.2 Demography and Baseline Characteristics**

Demographic variables and baseline characteristics will be summarized by treatment group and overall. Summary statistics will be presented for metric variables. Frequency tables will be presented for categorical variables.

Demography includes age, gender, race, ethnicity, region, body height, body weight, body mass index (BMI), smoking history, and alcohol consumption. Age and BMI will each be given as continuous variable and categorized with the following categories:

- Age (years): <65, 65-75, >75
- BMI (kg/m^2): ≤30, >30.

The following additional baseline characteristics will be analyzed:

- Time from the qualifying HF event to randomization (days, continuous)
- Qualifying HF event: Hospitalization, IV diuretic
- LVEF (%) at baseline: 45% - <50%, 50% - <60%, ≥60%
- NT-proBNP (pg/mL) at baseline (continuous)
- eGFR (mL/min/1.73m^2) at baseline (continuous)
- eGFR (mL/min/1.73m^2) at baseline: ≤60, >60
- Heart rhythm: Atrial fibrillation, Sinus rhythm
- SBP (mmHg) at baseline (continuous)
- SBP (mmHg) at baseline: <120, ≥120
- Diastolic blood pressure (DBP; mmHg) at baseline (continuous)
- Heart rate (HR; beats/min) at baseline (continuous)
- NYHA class at baseline: Class II, III
- Medical history of coronary artery disease (CAD): present, not present
- Medical history of diabetes mellitus: diabetes, no diabetes
- Medical history of atrial fibrillation: yes, no
- Medical history of arterial hypertension: present, not present
- Medical history of chronic kidney disease (CKD): present, not present
- Medical history of chronic obstructive pulmonary disease (COPD): present, not present
- Medical history of anemia: present, not present

Demographics and baseline characteristics tables will also be presented by the subgroups defined in Section 4.4.4.

### **6.1.3 Protocol deviations**

The number of patients with validity findings and important deviations will be presented overall and by investigator and country for each treatment group and in total. The frequencies of each major protocol deviation will be presented by treatment group and total.

### **6.1.4 Medical History**

Medical history findings will be coded by Medical Dictionary for Regulatory Activities (MedDRA) codes. Medical history will be presented for each MedDRA Primary System Organ Class (SOC) and Preferred Term (PT) by treatment group and overall.

### **6.1.5 Concomitant Medication**

Prior and concomitant medications will be coded by Anatomical Therapeutic Chemical (ATC) classification system according to the World Health Organization Drug Dictionary (WHO-DD).

#### **6.1.5.1 Selected Concomitant Medication of Special Interest**

Concomitant medication of special interest, derived via ATC codes, Bayer Drug Grouping (BDG), or combinations of both ATCs and BDGs, will be summarized by class and corrected generic name. Of special interest are the drug groups:

- diuretics
- $\beta$ -blockers
- ACE inhibitors
- Angiotensin receptor blockers (ARB)
- Mineralocorticoid receptor antagonists (MRA)
- SGLT-2 inhibitors
- Calcium channel blockers

Diuretics will be categorized into the subcategories loop diuretics, thiazides, and potassium sparing diuretics. In addition the combined drug group ACE inhibitor and/or ARB will be analyzed.

The number of patients taking a medication in a drug group of special interest or combination of concomitant medications of special interest at any time during the study will be given. In addition, the number of patients taking a medication in a drug group of special interest at baseline and week 24 will be given. Medication start and stop date information will be used to assess, if a medication was taken at the respective visits. In addition, the tables with number of patients taking a medication in a drug group of special interest at baseline (Day 1) will be provided for the subgroups specified in Section 4.4.4.

A cross-tabulation comparing the number of patients taking a combination of concomitant medications of special interest at baseline 1 and the number of patients taking individual drug groups of interest at week 24 will be presented by treatment group.

### **Analysis of diuretics**

An analysis of percentage of equivalence dose taken will be performed. Percentage of equivalence dose is calculated individually per subject and medication as:

$$\text{Percentage of equivalence dose} = \text{actual dose} / \text{equivalence dose} * 100$$

In case of missing dose and/or frequency information, the respective medication will be omitted from the analysis. Percentage of equivalence dose will be calculated for medications taken at baseline and week 24.

In case a subject takes several medications from one diuretics subcategory at a visit, the sum of the percentages of equivalence dose of the different medications will be used for the subject for the respective visit.

For each diuretics subcategory, summary statistics will be provided for percentages of equivalence dose as well as changes from baseline in percentages of equivalence dose by treatment group and overall.

In addition, patients will be grouped into 'below 50% of equivalence dose', '50% to 100% of equivalence dose', 'more than 100% of equivalence dose' and 'no respective medication intake'. For each diuretics subcategory, number and percentage of patients within each percentage group will be given by treatment group and overall at baseline and week 24.

Changes from baseline to week 24 will be categorized into the categories 'dose increased', 'dose not changed', 'dose reduced', 'new drug started', 'drug intake stopped'.

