7.1 Treatments to be administered

Patients will be randomized 1:1:1 within 4 weeks after the Screening Visit to either:

1. Placebo arm: placebo and sham up-titration at weeks 2, 4, and 6
2. 10 mg arm: vericiguat, which will be started at 2.5 mg at randomization and up-titrated to 5 mg at week 2, and to 10 mg at week 4, with sham titration at week 6.
3. 15 mg arm: vericiguat, which will be started at 2.5 mg at randomization and up-titrated to 5 mg at week 2, to 10 mg at week 4, and to 15 mg at week 6.

Study drug treatment will be initiated after clinical stabilization, within 6 months after the onset of the qualifying HF decompensation, defined as HF hospitalization or IV diuretic treatment for HF without hospitalization. End of treatment is reached at visit 9 after 24 weeks of treatment.

Dose modification will depend on mean sitting SBP and the absence of symptoms indicative of hypotension before intake of the dose as described in Section 7.4. The intention of the protocol is to reach and maintain the target study drug dose upon uptitration. If the patient does not reach the 15 mg dose step by the time of the week 6 visit (42±3 days after randomization), or the dose is temporarily interrupted and when the investigator feels it is medically appropriate to resume it afterwards, uptitration should be considered at any subsequent visit at the discretion of the investigator according to the SBP criteria in Section 7.4.

If in the opinion of the investigator the patient does not tolerate the target dose of the study drug and presents symptoms of orthostatic hypotension, in addition to considering the reduction of the study drug the investigator should also consider the volume status, and whether there is a necessity to change the dose of diuretics. If such adjustment or discontinuation of concomitant diuretic or other medications (such as anti-hypertensive therapy, in the case of excessive blood pressure lowering) is not possible or does not resolve signs and symptoms of intolerance, the investigator may at any time during the course of the trial reduce the dose or interrupt study treatment in patients who no longer tolerate the current study drug dose.

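### SAP 6.1.5.1 drops diuretics of unknown dose from the summed percentage and has no class for patients taking them, so the dose and dose-change tables can misstate or fail to place these patients

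*SAP*

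**What the plan says.** SAP 6.1.5.1 (Analysis of diuretics) expresses each diuretic as a percentage of the daily equivalence dose in Table 6-1, at baseline and at week 24. Four rules matter here.

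- **Missing dose or frequency.** "In case of missing dose and/or frequency information, the respective medication will be omitted from the analysis".
- **Several drugs in one subcategory.** "the sum of the percentages of equivalence dose of the different medications will be used for the subject for the respective visit".
- **Dose groups.** "patients will be grouped into 'below 50% of equivalence dose', '50% to 100% of equivalence dose', 'more than 100% of equivalence dose' and 'no respective"; the last label, cut short here, is the class for patients with no intake of that kind of drug.
- **Change categories from baseline to week 24.** "dose increased', 'dose not changed', 'dose reduced', 'new drug started', 'drug intake stopped".

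Earlier in 6.1.5.1, under selected concomitant medication of special interest, intake at a visit is settled without reference to dose: "Medication start and stop date information will be used to assess, if a medication was taken at the respective visits". The same text plans simple intake counts: "the number of patients taking a medication in a drug group of special interest at baseline and week 24 will be given".

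SAP 6.1 makes the FAS (all randomized patients) the default set for these tables. It does not say how the week-24 and change tables treat patients who are no longer in the study.

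**The concern.** The omission rule removes a drug that the patient is known to be taking, and the patient must then be placed in lists that have no class for unknown dose and none for a change that cannot be evaluated. Missing information can therefore show up as a low dose or as a change in treatment.

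The table has a purpose in this trial. When the target dose is not tolerated and there are symptoms of orthostatic hypotension, Protocol 7.1 asks the investigator to consider "whether there is a necessity to change the dose of diuretics". Protocol 8.1 lets diuretics be changed whenever the investigator finds it necessary. Symptomatic hypotension is an event of special interest (SAP 6.3.2). Diuretic adjustment could thus differ between arms, and this is the only analysis in the SAP that shows diuretic dose and dose change by arm. A reader of the study report would use it when interpreting hypotension or congestion.

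**Working it through.** The plan states no figure on this point, so there is nothing to reproduce. The check applies the written rules to illustrative patients.

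**Inputs.** Equivalence doses from SAP Table 6-1: furosemide 40 mg daily and torsemide 10 mg daily, both loop diuretics. Each patient takes the same drugs at the same doses at both visits, so the true change is always none.

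**Formula.** Percentage = actual dose / equivalence dose × 100, summed within the subcategory. Furosemide 40 mg gives 40/40 × 100 = 100%. Torsemide 10 mg gives 10/10 × 100 = 100%. Both together give 200%.

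**Reading A: an omitted drug is treated as absent.**

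| Patient | Dose unknown at | Baseline | Week 24 | Change shown |
|---|---|---|---|---|
| Furosemide only | week 24 | 100% | no intake | stopped |
| Furosemide only | baseline | no intake | 100% | started |
| Furosemide only | both visits | no intake | no intake | no category fits |
| Both drugs, torsemide dose unknown | week 24 | 200% | 100% | reduced |
| Both drugs, torsemide dose unknown | baseline | 100% | 200% | increased |
| Both drugs, torsemide dose unknown | both visits | 100% | 100% | not changed |

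In the last row the change is right but the dose group is wrong: the patient belongs above 100% and is shown in the 50% to 100% group at both visits.

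**Reading B: the date rule decides intake in these tables too.** The furosemide-only patients are then taking the drug at both visits. They are not untreated, started or stopped, but with no usable dose they also fit none of the three dose bands, and cannot be called increased, unchanged or reduced. The SAP does not say whether they leave the table or remain in the denominator.

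The two-drug rows are the same under both readings. Those patients count as taking a loop diuretic either way, and the sum still lacks one drug. The understated percentage and the false change therefore follow from the rules as written, whereas the one-drug outcome depends on which reading the programmer adopts.

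**Consistency within 6.1.5.1.** Under reading A, the no-intake counts in the dose-group table can contradict the date-based intake counts planned in the same section. Under reading B they agree, but the list of classes is incomplete.

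**The case against.** The strongest reply is that the SAP never says a patient with an omitted drug becomes untreated, started or stopped. The omission sits in an analysis of percentage of equivalence dose, and the section already decides intake by dates. That stands: a reader might infer that every such patient is counted as off treatment or as having changed treatment, and the documents do not support so firm a statement. What remains is that a one-drug patient has no class under the date rule, and that the two-drug error does not depend on the reading.

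A reader might also try to put a rate on false starts and stops. Suppose a share L of patients takes a loop diuretic unchanged and a share p of records lacks a dose, independently at each visit. The false share in each direction is then L × p × (1 − p). With L = 60% and p = 2% this is 0.60 × 0.02 × 0.98 = 1.2%; with L = 80% and p = 10% it is 0.80 × 0.10 × 0.90 = 7.2%. None of these inputs is in the documents, and the independence assumption fits poorly. An unchanged diuretic would normally be one ongoing dated record, with its dose missing at both visits or at neither, and that produces no false start or stop. A false change needs separate records of differing completeness, for example a new record without a dose after an adjustment.

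A third inference is that patients who died or withdrew are counted as still treated, or as stopped. That depends on how medication records are closed at exit, which the documents do not describe. Only the absence of a stated rule for these patients can be shown.

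Finally, the tables are descriptive, the date-based intake counts need no dose, and Protocol 11.1 describes data-entry checks for completeness. All of this is right, and it limits the weight of the point.

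**Conclusion.** The point holds as a minor defect in a descriptive analysis. For a patient on two or more drugs of one subcategory with one dose unknown, the rules give an understated percentage, and a false reduction or increase if the dose is unknown at only one visit. For a patient whose only drug in the subcategory has an unknown dose, the rules give either a class that conflicts with the date-based intake rule or no class at all.

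The size cannot be computed: the documents give no rate of missing dose or frequency and no share of patients on more than one drug of a subcategory. Nothing in them shows that missing doses would differ by arm. The effect is confined to the percentage-of-equivalence-dose summaries, the dose groups and the change categories. The date-based intake counts, the KCCQ PLS analysis and the 6MWT analysis are untouched.

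**What to change.** Amend SAP 6.1.5.1 as follows.

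1. State that the date rule already used for intake at a visit also decides the no-intake group and the started and stopped categories in the diuretic tables, whether or not the dose is known.
2. If any drug in a subcategory has unknown dose or frequency at a visit, set that patient's summed percentage for that visit to missing. Report the patient in a new dose group, 'taking, dose unknown'. If the patient is taking a drug of the subcategory at both visits and either sum is missing for this reason, report the change as 'not evaluable'.
3. State the denominator for the week-24 and change tables, and show patients no longer in the study on a separate line.

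This needs a few lines of SAP text and minor programming, with no new data and no change to any clinical rule. The cost is that fewer patients contribute to the numeric summary of change in percentage of equivalence dose. The added classes show how many are affected in each arm.

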**Table 6-1: Equivalence doses for different diuretics**

Diuretic (ingredient)	Daily Equivalence* Dose (mg)
Loop diuretics	
Bumetanide	1
Furosemide	40
Torsemide	10
Thiazides	
Bendroflumethiazide	2.5
Hydrochlorothiazide	12.5
Indapamide	2.5
Metolazone	2.5
Potassium-sparing diuretics	
Amiloride	5 # or 10 †
Spironolactone/eplerenone	50 # or 100 †
Triamterene	100 # or 200 †

\*in combination with ACEi and/or ARB. †without ACEi and ARB.

\*Equivalence does not mean bio-equivalence.

Daily equivalence doses are taken from table 16 in the ESC HF Guideline 2012 [18].

### 6.1.6 Treatment Duration and Exposure

Treatment duration (number of days with study treatment intake, calculated based on the start and stop dates of tablet intake, not including interruptions of drug) will be summarized using descriptive statistics by treatment group and overall. In addition, treatment duration will be categorized to  $\leq 7$  days,  $>7-42$  days,  $>42-84$  days,  $>84-126$  days,  $>126-168$  days, and presented with the corresponding number and percentage of patients by treatment group and overall. A table will be presented with the absolute and relative frequencies of patients still in the study at each visit. Kaplan-Meier plots for time-to end of study treatment will be provided for each treatment group. The extent of exposure to study treatment (total amount of intake in mg) will be summarized using descriptive statistics and by 200-mg intervals by treatment group and overall.

Gaps as well as interruptions will not be counted towards duration calculations. Overlaps will be handled by setting the first record with overlap as the day before the start of the following record. The exposure will be computed as the total dose assumed record by multiplying the treatment days by the relative dose and summing them across days on treatment for each individual patient.

### 6.1.7 Treatment Compliance

The compliance will be summarized descriptively by treatment group and overall. In addition, compliance will be categorized into three groups (<80%, 80-120%, >120%) and summarized by treatment group and overall.

Compliance will be calculated as the number of tablets taken divided by the number of tablets dispensed \* 100. In addition:

- 1) If the patient is missing return tablets or missing dispensing tablets then those tablets are not counted toward the number of tablets taken for the compliance calculation.
- 2) If the dispensing or return dates are missing but the number of return and dispensing tablets are present, the number of tablets taken will be considered for the compliance calculation.
- 3) Missing compliance will be noted as missing instead of 0.

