9.2.6 Visit 6 – Day 56±3 (week 8)

Patients need to come for this visit without taking the morning dose of the study drug (this applies only for the study drug. All others medications shall be taken as scheduled)

- Assessment of NYHA class
- Concomitant medications (see Section 8.1)
- Adverse events (see Section 9.6.1)
- Physical examination
- Vital signs (BP and pulse rate). See Section 9.7.5.
- Central lab blood samples for NT-proBNP, hematology, clinical chemistry, coagulation and biomarkers prior to study drug intake (exact collection time to be documented; see Section 9.7.1)
- Drug accountability, incl. exact time of last dose intake the day before, and collect unused study drug
- Optional uptitration/sham titration if not yet on target dose, dispense study drug in accordance with dosing regimen for the 6 week interval until Visit 7 and instruct the patient on how to take the study drug.
- Patient to take the study drug (exact time of intake must be documented)
- Only in case of uptitration from dose step 3 to dose step 4, 2 h ± 15 min after study drug intake: Vital signs BP and pulse rate). See Section 9.7.5.
- Schedule Visit 7 for Day 84±3
- Only for patients participating in the optional accelerometry substudy: activity tracking devices are planned to be handed out with instructions to use as specified in the accelerometry procedure manual.

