## **4.4 Data Rules**

### **4.4.1 Compliance**

The patient drug intake compliance is calculated as percent of planned tablet intake:

$$100 * \text{Number of taken tablets} / \text{Number of planned tablets}.$$

The *number of planned tablets* is calculated as: *Treatment duration (days) \* Number of planned tablets per day*. The *number of planned tablets per day* is two.

To derive *treatment duration*, the start and stop dates of tablet intake are derived from the collected study treatment exposure (dataset EX). The *number of taken tablets* is derived from the drug accountability (dataset DA).

For patients who withdraw prematurely from the study treatment, compliance will be calculated up to the time of last dose.

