## **7.     Document history and changes in the planned statistical analysis**

### **7.1     Document history**

- Version 1.0
- Version 2.0
  - Added updates per the FDA Type C meeting held on 11/6/2019
  - Added definition of completer
  - Updated definition of baseline, treatment compliance calculation , and treatment duration calculation
  - Updated with latest SAS code
  - Included imputation rules for partially missing end dates for study medication

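### SAP 4.4.1 and 6.1.7 define compliance with different denominators; under 6.1.7 a patient who misses no dose but stops soon after a dispensing visit can score below 80%

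*SAP*

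**What the plan says.** SAP 4.4.1: "The patient drug intake compliance is calculated as percent of planned tablet intake". Planned tablets are treatment duration in days times two. The number taken "is derived from the drug accountability (dataset DA"). For early stoppers: "For patients who withdraw prematurely from the study treatment, compliance will be calculated up to the time of last dose".

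SAP 6.1.7: "Compliance will be calculated as the number of tablets taken divided by the number of tablets dispensed", times 100. The result is tabulated by arm as <80%, 80-120% and >120%. Three data rules follow:
- Rule 1: where a return or dispensing count is missing, "those tablets are not counted toward the number of tablets taken for the compliance calculation". The denominator is not mentioned.
- Rule 2: "If the dispensing or return dates are missing but the number of return and dispensing tablets are present", the tablets do count as taken.
- Rule 3: missing compliance is reported as missing, not as zero.

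Related text:
- Protocol 7.7 sets the 80-120% target against scheduled intake and determines accountability by tablet count at each visit.
- SAP 5.1.6 excludes patients below 80% or above 120% overall compliance from the per-protocol set (PPS) and names no formula.
- SAP 6.1.6 excludes gaps and interruptions from treatment duration.
- SAP 7.1 lists for version 2.0: "Updated definition of baseline, treatment compliance calculation , and treatment duration calculation". It does not say which section carries the update. SAP 7.1.1 records no changes from the protocol.

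**The concern.** One measure has two formulas in the same version of the SAP, and a programmer cannot tell which to use. They are not interchangeable. The 4.4.1 formula asks what share of the scheduled tablets was taken while the patient was on treatment. The 6.1.7 formula asks what share of the tablets handed out was used, so the score also depends on how long after the last dispensing visit the patient stopped. If the arms differ in when patients stop, the 6.1.7 table could show an apparent difference in adherence where none exists. The 80-120% band also fits poorly with a ratio that cannot pass 100%. PPS membership is at stake as well if 6.1.7 is the formula applied to the compliance exclusion.

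**Working it through.** The plan gives no computed compliance figure to reproduce, so the check applies both formulas to the same patient.

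**Inputs**
- Two tablets a day (SAP 4.4.1; protocol 7.3 and 7.4).
- Dispensing at Visits 2 to 8 (protocol 7.7), scheduled on days 1, 14, 28, 42, 56, 84 and 126, with end of treatment on day 168 (protocol Table 9-1).
- Pack size is not stated. Assumption: each pack covers the scheduled interval to the next visit (14, 14, 14, 14, 28, 42 and 42 days), with no spare tablets, visits on schedule, and a new pack counted from the day after the visit. Cumulative supply is then 14, 28, 42, 56, 84, 126 and 168 days, or 336 tablets in all.
- The patient misses no dose up to stop day *t*, so tablets taken = 2*t*.

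**Upper bound under 6.1.7.** The SAP does not write out how tablets taken are obtained. Drug accountability as the source, and rules 1 and 2, point to dispensed (D) minus returned (R). Then (D − R)/D ≤ 1, so the ratio cannot exceed 100% apart from count errors, and the >120% class cannot be reached.

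**Early stoppers.** 4.4.1 gives 2*t*/(2*t*) = 100% on every day. 6.1.7 gives *t* divided by the cumulative days dispensed:

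| Stop day | 6.1.7 | 4.4.1 |
|---|---|---|
| 60 | 60/84 = 71.4% | 100% |
| 91 | 91/126 = 72.2% | 100% |
| 130 | 130/168 = 77.4% | 100% |

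**Dependence on supply.** Protocol 9.2.6 says to "dispense study drug in accordance with dosing regimen for the 6 week interval until Visit 7", but schedules Visit 7 for day 84, which is 84 − 56 = 28 days later. If 42 days were supplied at Visit 6, cumulative supply from that visit becomes 98, 140 and 182 days. The three scores become 60/98 = 61.2%, 91/140 = 65.0% and 130/182 = 71.4%. A completer who misses no dose would score 336/364 = 92.3%, still in the band. Spare tablets would lower 6.1.7 scores further.

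**How often the score falls below 80%.** Over stop days 1 to 167, 6.1.7 is below 80% on 61 days with the 28-day Visit 6 supply and on 94 with the 42-day supply. If a new pack counts from the visit day itself, the counts are 67 and 100. These counts depend on the assumed packs and are calendar days, not patients.

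**Rule 1.** Take a fully adherent completer with no return count for the Visit 7 or Visit 8 supply (42 × 2 = 84 tablets). With the denominator left unchanged, the score is (336 − 84)/336 = 252/336 = 75.0%. With the supply removed from both sides, it is 252/252 = 100%.

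**The case against.** The strongest reply is that this affects one descriptive table, with magnitudes that rest on assumed pack sizes. Much of that stands. Pack sizes are not given, the 42-day Visit 6 figures depend on protocol wording that conflicts with its own visit dates, and no discontinuation timing is available. What does not depend on pack size is that the two denominators differ and that 6.1.7 charges an early stopper for unused tablets.

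Four stronger readings are tempting, and the documents do not support them.
- A reader might infer that 6.1.7 hides over-use that 4.4.1 would expose. The band and the PPS rule use overall compliance. Even with the 42-day Visit 6 supply, a patient otherwise on schedule who used it all by day 84 would score (112 + 84)/168 = 116.7% under 4.4.1 at that point. A completer who took every tablet would score 364/336 = 108.3%, or 336/336 = 100% with the 28-day supply. Without spare tablets or interruptions, 4.4.1 passes 120% only for some early stoppers.
- A reader might infer that adherent early stoppers will be dropped from the PPS. SAP 5.1.6 names no formula, the full exclusion list is in the Assessment Criteria Identification Requirement (ACIR), which is not available here, and SAP 5.1 leaves assignment to the validity meeting.
- A reader might take the day counts as a share of patients. They are not.
- A reader might take 75.0% as the result of rule 1. It holds only if the denominator is left alone; dropping the supply from both sides is an equally available reading.

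It can also be said that 6.1.7 may be the version 2.0 update, so preferring 4.4.1 is a choice. The history does not settle this. Protocol 7.7 favors 4.4.1, because it measures against scheduled intake. One caution remains: if the 6.1.6 definition of duration applies, 4.4.1 measures adherence only on days outside recorded interruptions, so it can be near 100% despite missed scheduled days. SAP 5.1.6 does have a separate exclusion for interruptions of more than 10 consecutive days.

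**Conclusion.** The inconsistency is real and minor. SAP 4.4.1 and 6.1.7 give different denominators for the same measure. The 6.1.7 version cannot reach its own top class, provided tablets taken means dispensed minus returned and counts are correct. It also puts some fully adherent early stoppers below 80%: 71.4%, 72.2% and 77.4% in the three examples, assuming packs sized to the scheduled interval. The compliance table by arm is affected for certain if 6.1.7 is programmed. PPS membership, and so the supportive analysis in SAP 6.2.3.2, is affected only if the same formula is used for the exclusion. If 4.4.1 is used there instead, the reported table and the PPS rule would disagree. The primary analysis on FAS (KCCQ) has no compliance criterion and is unaffected.

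**What to change.** - In SAP 6.1.7, replace the dispensed-based formula with a reference to 4.4.1.
- In SAP 5.1.6 and the ACIR, state that the <80% / >120% exclusion uses that value.
- In 4.4.1, state that the 6.1.6 definition of treatment duration (interruptions excluded) applies, or state the exception.
- In rule 1 of 6.1.7, remove a supply with a missing return count from both numerator and denominator, or set compliance to missing under rule 3.
- In SAP 7.1, record which section holds the version 2.0 calculation.

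Separately, the Visit 6 supply wording in protocol 9.2.6 and the visit dates need to be reconciled.

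The cost is a cross-reference, a few sentences and one derivation. No new data are needed. It is best done before unblinding.
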